## **10 DATA COLLECTION AND QUALITY ASSURANCE**

### **10.1 Data Collection Forms**

Information will be collected for each participant by the research assistant, [name] or the postdoctoral fellow, [name], who will be blinded to the treatment groups. Each participant will be assigned a study ID and the records identifying participant name will be kept confidential in a locked study cabinet at the study clinic at Jack Satter House and, to the extent permitted by the applicable laws and/or regulations, will not be made publicly available. Urine samples collected will not identify the participant and will include only participant ID. Identifiers will be removed before entering the data electronically in a password protected REDCap database. The results of the study will only be published or presented as group data. No individual participants will be identified. Forms to collect data will be identified with a unique study number and kept locked in the study office. Once the data is entered into the electronic database, all source documents will be stored in a locked cabinet in PI's office at Marcus

Institute, HSL for a period of 7 years. After that the identifying information will be shredded.

Subject records may be reviewed in order to meet federal or state regulations. Reviewers may include the HSL Institutional Review Board, or others in order to meet regulatory requirements.

## **10.2 Data Management**

[name] will be responsible for the overall operation of the study, including IRB approvals, preparing budgets, monitoring expenses, data analysis and preparation of summary of findings. [name] will be responsible for training of study staff and reviewing data for any inconsistencies, reviewing eligibility, adverse events, and laboratory values and assisting [name] with data interpretation and manuscript writing. [name] and [name] will oversee the research assistant, [name], the postdoctoral fellow, [name] as well clinical dietitian, [name].

Data will be managed with REDCap on a secure server. Embedded quality control procedures will be used to ensure data integrity. [name], [name], or the postdoctoral fellow, [name] will collect all data, enter into REDCap database, work with Drs. [name] and [name] to complete quality control processes. Data will be stored on a secure server behind HSL's firewall. [name], [name] and [name] will fill complete the follow-up visit 1 and the completed forms will be kept in a locked cabinet at Jack Satter House by [name] until they are ready to be entered into REDCap. Once the data is entered electronically, all source documents will be kept in a locked cabinet in [name] office at the Marcus Institute. Safeguards to be used include keeping the source documents locked to protect participant privacy. We will also have a quality control process in place once the data is entered in REDCap. [name] will review the laboratory values of urine test and will also review the sources data for any inconsistencies. Data will be explored for potential outliers before the analysis.

## **10.3 Quality Assurance**

### **10.3.1 Training**

Describe types and mechanisms of training of staff for the study. [name] and [name] both participated in training at HSL in the TUG test procedure by a content expert. Subsequently both attended two extended practice sessions where each of them tried out each aspect of the procedure at the study site location.

[name] and [name] have completed an online training in administration of the MoCA standardized test.

[name] and [name], an experienced clinical nurse specialist and research program manager, led [name] and Drs. [name] and [name] through the process of obtaining height, weight, seated and orthostatic blood pressure measurements, with two practice sessions. [name] also trained [name] and [name] in infection control practices including cleaning frequently used equipment, and collection and processing of urine samples. [name] also practiced use of all data collection forms under Drs. [name] and [name]'s guidance.

### **10.3.2 Quality Control Committee**

For this pilot study there is no quality control committee. Responsibility for oversight of quality control rests with the PI or designated co-investigator.

### **10.3.3 Protocol Deviations**

In the event of a protocol deviation, [name] or [name] will report to [name] with details of the event. The deviation report will be filed with the HSL IRB. In the event of possible injury to a participant from a study deviation the study physician will review the file and may follow up directly with the participant, and their primary care or other clinician to ensure referral for any care needed.

### **10.3.4 Monitoring**

At each visit [name] or [name] will complete a summary checklist of all items to be done during the visit. Once consent has been obtained, [name] or [name] will add a check of consent at the start of each visit, prior to any data collection. [name] or [name] will review participant's data with [name] or [name] weekly to determine eligibility and once enrolled, participant safety.

No site monitoring will be done during the pilot.

## **11 PARTICIPANT RIGHTS AND CONFIDENTIALITY**

### **11.1 Institutional Review Board (IRB) Review**

This protocol and the informed consent document (Appendix 1) and any subsequent modifications will be reviewed and approved by the Hebrew SeniorLife IRB committee responsible for oversight of the study.

### **11.2 Informed Consent Forms**

A signed consent form will be obtained from each participant. The consent form is only available in English at this time. The majority of residents at Jack Satter House are English speaking. At the request of a participant the research assistant will read the consent to them (for persons with visual difficulty or lower literacy). The consent form will describe the purpose of the study, the procedures to be followed, and the risks and benefits of participation. A copy will be offered to each participant and this fact will be documented in the participant's record.

### **11.3 Participant Confidentiality**

All personal information obtained in the study will be kept confidential, and this information will only be available to the research staff. The records identifying the name of participants will be kept confidential in a locked study cabinet at the study clinic at Jack Satter House and, to the extent permitted by the applicable laws and/or regulations, will not be made publicly available.

To protect confidentiality, forms used to collect data will be identified with a unique study number and kept locked in the study office before entering the data electronically in a secure REDCap

database stored on the Hebrew SeniorLife servers. The results of the study will only be published or presented as group data. No individual participants will be identified.

Identifiable private information collected from participants during this study may be used for future research studies or shared with other researchers for future research. The identifiable private information may be used for future research of blood pressure management and falls. If the research investigator distributes information to other researchers or institutions, participant's identity will be concealed with a research code without identifiers so that they cannot be identified. No additional consent will be requested for the future use of participant's information. No biological specimens will be stored as part of this study.

Records may be reviewed in order to meet federal or state regulations. Reviewers may include representatives from the Study Sponsor and the HSL Institutional Review Board, or others in order to meet regulatory requirements. Protected health information may be reviewed by the clinical laboratory performing urine testing for this study. Information will not be released without written permission of the participant, except as necessary for monitoring by IRB, the FDA, the NIA, and the OHRP.

#### **11.4 Study Discontinuation**

The study may be discontinued at any time by the IRB, the Sponsor, the NIA, the OHRP, the FDA, or other government agencies as part of their duties to ensure that research participants are protected.

## **12 ETHICAL CONSIDERATIONS**

This research project will follow the seven guiding ethical principles published by the NIH:

- Social and clinical value
- Scientific validity
- Fair subject selection
- Favorable risk-benefit ratio
- Independent review
- Informed consent
- Respect for potential and enrolled subjects

The intent is to answer the specific questions posed in this project using a scientifically valid method, with the collaboration of well-informed research participants who have been fairly selected. The risk versus benefit ratio in this project has been carefully reviewed by both internal and sponsor's independent review to maximize participant safety. The findings of this project will be disseminated via publication in scientific journals.

### 14 **PUBLICATIONS AND RESEARCH FINDINGS**

Publication of the results of this trial will be governed by the policies and procedures developed by the Steering Committee, and more generally by [Harvard Medical School's Policy on Authorship](#). Any presentation, abstract, or manuscript will be made available for review by the sponsor and the NIA prior to submission.

SOTRUE

STATISTICAL ANALYSIS PLAN

VERSION 1.0

October 29, 2019

Table of Contents

1	Introduction.....	3
	Primary aim.....	3
	Other aims.....	3
2	Data Source.....	4
3	Primary Outcome: Serum Uric Acid.....	5
	Randomization and primary analysis.....	5
	Power and sample size.....	5
	Pre-specified Stratified Analysis.....	5
	Sensitivity analyses.....	6
4	Other outcomes	6
	Analysis	6
5	Missing data.....	8
6	Safety outcomes	9
7	References.....	10

1 Introduction

SOTRUE is an individual level, randomized feeding trial to determine the effect of 2 weeks of low sodium meal plan on seated blood pressure in 45 adults over the age of 60 years. Participants are randomly assigned to one of 2 meal plans: (1) Low sodium meal plan or (2) usual meal plan.

The **primary outcome** is the net effect of reduced sodium versus usual diet on 2-week seated blood pressure.

1.1 Primary aim

To determine the effects of a low sodium (<0.9 mg per kcal of energy intake), 2-week meal plan compared with a usual meal plan (average sodium ~2 mg per kcal of energy intake) on seated BP among independently living older adults. In this randomized controlled trial (RCT) of 45 patients, we will compare a low sodium diet intervention vs. usual sodium diet over 2 weeks to determine the effect of the sodium reduction on seated blood pressure.

1.2 Other aims

To estimate the effects of the low sodium diet on the following outcomes as well the variances of these outcomes:

- A. Seated diastolic blood pressure
- B. Standing blood pressure
- C. Orthostatic hypotension (OH)
- D. Timed Up and Go
- E. Urinary sodium, potassium, and creatinine excretion
- F. Orthostatic symptoms

2 Data Source

Data will be entered by clinic staff into a REDCap dataset. Meal nutrient information will be derived from the Computrition platform. Backup files of the database will be generated and stored at regular intervals in a secure, off-site location, to permit regeneration of the database in the event that it is destroyed.

3 Primary Outcome: Seated Blood Pressure

3.1 Randomization and primary analysis

Participants will be randomized using a computer-generated randomization scheme with varying sized blocks to 1 of 2 meal plans in a 1:1 ratio such that approximately half of participants will undergo the low sodium diet intervention, while the other half will undergo the usual sodium meal plan intervention. Sex will be used as a stratification variable to ensure that sex is evenly distributed between interventions.

We will first confirm that the residuals of seated blood pressure are normally distributed (if not then it will be log-transformed). We will compare net effect of reduced sodium versus usual diet on 2-week seated blood pressure. This comparison will be performed by fitting a linear regression model with adjustment for baseline seated blood pressure. We will perform an intent-to-treat analysis.

Our hypothesis is that 2-weeks of a low sodium meal plan intervention will lower seated blood pressure compared to 2-weeks of a usual sodium diet. The null hypothesis is that there will be no difference in seated blood pressure between the two intervention arms. The comparison between the two treatment groups will be performed by comparing the regression coefficient for treatment with zero (two-sided Wald test at 0.25 significance level to avoid type II error)¹ using linear regression with adjustment for baseline blood pressure.

Our primary outcome will be the average of two systolic blood pressures measured on days 12-15 of the study period. A sensitivity analysis will be performed examining the last systolic blood pressure measurement.

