### **9.5 Data Analyses**

#### **Primary analysis**

We will first confirm that the residuals of seated blood pressure are normally distributed (if not then it will be log-transformed). We will compare net effect of reduced sodium versus usual diet on 2-week seated blood pressure. This comparison will be performed by fitting a linear regression with adjustment for baseline seated blood pressure. We will perform an intent-to-treat analysis.

Our hypothesis is that 2-weeks of low sodium dietary intervention will lower seated blood pressure compared to 2-weeks of usual sodium diet. The null hypothesis is that there will be no difference in seated blood pressure between the two intervention arms. The comparison between the two treatment groups will be performed by comparing the regression coefficient for treatment with zero (two-sided Wald test at 0.05 significance level).

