3.2 Power and sample size

To detect the 2-week difference in seated SBP (primary outcome) observed in the DASH-Sodium trial² (-9.53 mm Hg, standard deviation of 10.46, a type 1 error of 0.05 with 80% power), we need 20 people in each arm (total 40). We will recruit 45 participants to account for a 10% attrition rate. Effect size and variance for the other endpoints (especially OH) will be used to inform power calculations for subsequent proposals.

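### The primary SBP analysis may move from mm Hg to the log scale on a residual check with no criterion; fixing the scale in mm Hg costs nothing and secures the estimand

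*SAP*

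**What the plan says.** SAP 3.1 opens the primary analysis with a check that the residuals are normal and sets the consequence of failure: "if not then it will be log-transformed". Protocol 9.5, under Primary analysis, has the same rule: "residuals of seated blood pressure are normally distributed (if not then it will be log-transformed". The model in the SAP is obtained by "fitting a linear regression model with adjustment for baseline seated blood pressure", and the outcome is defined there as follows: "Our primary outcome will be the average of two systolic blood pressures measured on days 12-15 of the study period".

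SAP 3.2 sizes the trial on an untransformed difference: a fall of "9.53 mm Hg, standard deviation of 10.46, a type 1 error of 0.05 with 80% power", giving 20 per arm and 45 recruited after allowing for 10% attrition.

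For the primary endpoint, neither document states:
- the test, plot or cut-off by which normality is judged;
- whether baseline pressure is logged as well;
- how a log-scale effect is to be reported or converted back;
- that a mm Hg estimate is still produced after a switch.

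The sensitivity analyses (SAP 3.4; protocol 9.5) vary the baseline adjustment, the on-treatment subset and, in the SAP, the use of the last reading alone. None brings back the untransformed analysis. For secondary endpoints, SAP 4.2 does give percentage-change reporting and a non-parametric fallback. The primary endpoint has neither.

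**The concern.** On the raw scale the treatment coefficient is a difference in mean SBP in mm Hg. On the log scale it becomes a ratio of geometric means. These are different estimands, and the plan lets the outcome data choose between them with no stated criterion, so two careful analysts could report the same trial on different scales.

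The mm Hg difference and its SD are also what the power statement uses, and what a later, definitive trial would need from a pilot. If the switch happens, nothing in the plan requires them to be reported. What is at stake is a fixed and readable primary estimate. Whether the test itself also suffers is a separate question, checked below.

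**Working it through.** **1. The plan's own figure.** Inputs from SAP 3.2: difference 9.53 mm Hg, SD 10.46, two-sided alpha 0.05, power 80%.

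n per arm = 2 × [SD × (1.960 + 0.842) / difference]² = 2 × [10.46 × 2.802 / 9.53]² = 18.9, so 19 by the normal approximation. The exact two-sample t calculation gives 19.92, so 20 per arm, with 80.2% power at 20. For attrition, 40 / 0.90 = 44.4, so 45. The stated sample size reproduces, and it is a calculation in mm Hg.

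**2. What the log does to the effect.** Take an assumed usual-diet mean of 125 mm Hg. A fall of 9.53 is a ratio of (125 − 9.53) / 125 = 0.924. Applied at other pressures:
- at 100 mm Hg: 100 × (0.92376 − 1) = −7.6 mm Hg;
- at 149 mm Hg: 149 × (0.92376 − 1) = −11.4 mm Hg.

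A ratio converts to mm Hg only at a stated reference pressure.

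**3. Is the switch needed?** A simulation of 6,000 trials per setting used 20 per arm and a linear model of follow-up SBP on arm and baseline. These assumptions are not in the documents: baseline mean 128, SD 12, limited to 100–149; slope 0.6; residual SD 10.46; switch to log SBP if Shapiro-Wilk gives p < 0.05; baseline left unlogged. Ranges cover effects of 0 and −9.53 mm Hg.

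| Residual shape | Switch triggered | Log then passes the check | Type I error, mm Hg model (0.05 / 0.25) | Power at 0.05: mm Hg model / with switch |
|---|---|---|---|---|
| Normal | 4–5% | 31–36% | 0.052 / 0.244 | 0.790 / 0.790 |
| t, 5 df | 28% | 18–20% | 0.049 / 0.255 | 0.796 / 0.794 |
| t, 3 df | 51–52% | 8–10% | 0.046 / 0.258 | 0.830 / 0.827 |
| 5% outliers | 29–30% | 16–17% | 0.049 / 0.250 | 0.797 / 0.794 |
| Right skew 1 | 49–50% | 37% | 0.053 / 0.262 | 0.796 / 0.812 |
| Exponential (skew 2) | 96% | 3–4% | 0.048 / 0.245 | 0.799 / 0.836 |
| Left skew 1 | 50% | 0–1% | 0.051 / 0.253 | 0.792 / 0.764 |

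Both significance levels appear because protocol 9.5 tests at 0.05 while SAP 3.1 specifies a "two-sided Wald test at 0.25 significance level to avoid type II error". That conflict is a separate matter, and the result here is the same at either level. With the switch in place, type I error was 0.046–0.054 at 0.05 and 0.243–0.265 at 0.25.

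**4. Mild right skew.** A second set of assumptions (baseline uniform on 100–149, slope 0.5, 3,000 trials) added gamma errors with skewness 0.5. The check triggered in 16% of trials, and the log then passed in about 59% of those.

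**5. How often the decision changes.** Under the second set of assumptions, with normal, t (4 df) and gamma-skewed errors, the decision at 0.05 differed between the fixed mm Hg model and the switching rule in 0.1% to 2.8% of trials. At 0.25 it differed in at most about 2% across the shapes tried. The exponential row above is the extreme: power moves by 0.836 − 0.799 = 3.7 points, so at least that share of decisions changes there.

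**The case against.** The rule is written in advance, names a single transformation and is the same in both documents. Checking residuals and taking logs if needed is common practice, and this is a pilot. All of that stands. The gap is a missing criterion and a missing mm Hg estimate, not an absence of planning.

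Four stronger readings are tempting, and none is supported:
- **That the scale is chosen with the treatment effect in view.** The documents do not show this. The check is placed first, and residuals can be examined without looking at the coefficient or from a model that omits arm. The plan is silent on how it will be done.
- **That a log cannot help because eligible SBP is confined to 100–149 mm Hg.** That range is a baseline criterion and does not bound follow-up SBP. With mild right skew, the case a log is meant for, it usually does restore normality.
- **That a ratio cannot be compared with −9.53 mm Hg.** It can, at a stated reference pressure. What is lost is a single difference that applies throughout.
- **That the switch distorts the test.** The null hypothesis is the same on both scales, and type I error stays close to nominal.

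The trigger and pass rates also depend on assumed error shapes and an assumed test. Because the SAP averages two readings, real residuals may be better behaved than the harsher shapes here. With normal errors the switch occurs in only about 5% of trials.

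**Conclusion.** The point holds as a modest improvement to the plan. That the rule exists, has no criterion and leaves no mm Hg analysis follows from the text alone. That the switch is unnecessary rests on simulation under stated assumptions: 20 per arm, residual SD 10.46, Shapiro-Wilk at 0.05. For every shape tried, the unswitched mm Hg model kept type I error close to nominal, and its power at 0.05 was 0.79–0.83.

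How well the log works varies with the shape. It fails in most triggered cases under heavy tails, left skew or right skew of 1 or more, and succeeds in most under mild right skew. A reader might infer that the primary p-value is at risk. It is not, to any material degree. The benefit of fixing the scale is a primary estimate known in advance to be a mm Hg difference, directly comparable with the planning value and usable for the next trial.

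**What to change.** In SAP 3.1 and protocol 9.5, state that the baseline-adjusted linear model of SBP in mm Hg is the primary analysis whatever the residual check shows, and remove the conditional transformation.

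Add two sensitivity analyses that are always run, so that neither depends on the residual check:
- a log-SBP model, saying whether baseline is also logged, with the effect given as a percentage change;
- a permutation test of the treatment effect, permuting within sex because sex stratifies the randomization.

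A heteroscedasticity-robust standard error would not replace these, since it addresses unequal variance rather than non-normality.

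The cost is a few sentences in each document and two short additional analyses. The sample size stays at 20 per arm, 45 recruited, and no data collection changes.

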## 3 STUDY DESIGN

- This is a placebo-controlled, double-blinded randomized controlled trial.
- Primary outcome includes seated blood pressure and secondary outcomes include orthostatic hypotension and timed up-and-go test.
- The study includes two arms (1) Low sodium meal plan and (2) Usual sodium meal plan. Forty participants will be enrolled in the study.
- Study population includes older men and women residing in the Jack Satter House, a congregate housing facility in Revere. Approximate duration of enrollment period and follow-up (specify individual participant vs. entire trial)

- After baseline data collection, participants will be randomized in a 1:1 ratio to 1 of 2 meal plans: a usual meal plan (this is the current meal plan with an average sodium intake of 2g per kcal of energy intake) or a low sodium meal plan (<0.9 g per kcal of energy intake similar to levels recommended by the American Heart Association recommendations). Both normotensive and hypertensive individuals will be recruited. Hypertension treatment will be considered as a pre-specified stratification variable.
- Urine will be collected from a random void at the baseline and follow up visits to measure sodium, potassium, and random creatinine. The samples will be sent to Quest Diagnostics Laboratories for analysis to measure excretion of these minerals pre and post exposure to the study diet. For urinary sodium the methodology used is ion selective electrode, with a reference range of 28 to 272 mmol/L. For urinary potassium sodium the methodology used is ion selective electrode, with a reference range of 12-129 mmol/L. For random urinary creatinine the methodology is kinetic colorimetry with a reference range for males of 20-320 mg/dl and females of 20-275 mg/dl.
- Quest Diagnostics is a nationally recognized CLIA certified laboratory capable of accurate and reproducible results on the analyses above. Reports are available electronically and will be uploaded directly into the statistical software at HSL via a CSV file.

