Randomization procedure: After baseline data collection, participants will be randomized in a 1:1 ratio to 1 of 2 meal plans: a usual meal plan or a low sodium meal plan. Randomization will be achieved using a web-based, password-protected, randomization software. While trial participants will know their intervention assignments, investigators and all study staff involved in baseline and follow-up data collection will be masked to participants' randomization assignments. Study staff involved in administering the dietary intervention and assessing compliance will be masked to participants' BP measurements. We will recruit the entire population cohort prior to initiating the intervention.

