#### Screening

**Visit 1. [Screening (SV) and initial baseline visit (BV1a)]:** Eligible participants will be undergo written informed consent. Questionnaire based information on demography, self-reported physical activity and medication list will be obtained for eligible participants as part of the initial baseline visit. Assessments of orthostatic hypotension, MoCA and seated blood pressure will be done at this visit to check for eligibility of the participant. Weight and height will be measured to calculate targeted caloric intake. This information will be needed in advance to prepare meals for the participants.

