### Baseline Assessments

For participants who have successfully been screened for eligibility and are enrolled into the study, baseline assessments will be performed against which to measure the study outcome. Run-In visit and baseline visit are described below.

- **Visit 2 [Randomization/baseline visit (RZ/BV1b)]:**
  - *Weight*
  - *Timed up and go test*
  - *Urine specimens*
  - *Symptoms and adverse events associated with sodium and orthostatic hypotension (headache, lightheadedness, dizziness, fatigue, etc.)*
- **Visit 3 [Run-In Visit, 1-2 days before meal delivery starts]:**
  - *Seated blood pressure*
  - *Weight*

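### The primary model omits sex, the factor that stratifies randomisation, and leaves baseline seated BP undefined although two pre-diet readings are collected.

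*SAP*

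**What the plan says.** **Randomisation.** SAP 3.1 states: "Sex will be used as a stratification variable to ensure that sex is evenly distributed between interventions". Protocol 9.2.1 agrees. Protocol 3 adds: "Hypertension treatment will be considered as a pre-specified stratification variable". Neither Protocol 9.2.1 nor SAP 3.1 repeats this.

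**Primary model.** SAP 3.1: "This comparison will be performed by fitting a linear regression model with adjustment for baseline seated blood pressure". Protocol 9.5 gives the same model. Sex enters only the subgroup models (Protocol 9.5, SAP 3.3), as a main effect plus an interaction with treatment.

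**Pre-diet seated BP.** There are two readings:
- Visit 1, screening, which is also called the initial baseline visit (Protocol 6.2.1): "Assessments of orthostatic hypotension, MoCA and seated blood pressure will be done at this visit to check for eligibility".
- Visit 3, under Baseline Assessments in Protocol 6.2.2: "Run-In Visit, 1-2 days before meal delivery starts".

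Visit 2, labelled baseline and randomisation, has no seated BP in the schedule (Protocol 6.1) or in the visit description.

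**Outcome.** SAP 3.1 makes it the average of two systolic readings late in feeding. The SAP gives no matching rule for the baseline covariate.

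**The concern.** There are two separate issues.

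1. Stratifying by sex balances the arms on sex. A model without sex leaves any sex-related variance in the residual, so the reported standard error takes no credit for that balance. If sex is prognostic, the interval is too wide and the test rejects too seldom under the null. SAP 3.1 says it wants to avoid type II error, and a needlessly conservative test works against that aim.

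2. The primary analysis rests on a covariate with at least three possible definitions: Visit 1, Visit 3 or their mean. In a trial of about 40 people the choice can move the result, and it should not be open once outcomes are known. A single reading is also a noisier measure of usual BP than two, so it removes less between-person variance.

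**Working it through.** **1. The plan's own figure.** SAP 3.2 sizes the trial on a fall of "9.53 mm Hg, standard deviation of 10.46, a type 1 error of 0.05 with 80% power", and states 20 per arm, with 45 recruited for 10% attrition.
- Normal approximation: 2 × [10.46 × (1.960 + 0.842) / 9.53]² = 18.9, so 19 per arm.
- Exact two-sample t-test: 78.0% power at 19 per arm and 80.2% at 20. The stated 20 reproduces.
- Attrition: 40 / 0.9 = 44.4, so 45. This reproduces.
- Planned SE: 10.46 × √(2/20) = 3.31 mm Hg. The 95% half-width is about 6.70 mm Hg.

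The documents do not say whether 10.46 is the SD of a final value, a change or a model residual.

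**2. Adding sex.** Let g be the sex difference in SBP left after baseline adjustment and s the residual SD. The Design and Outcomes section plans 75% women, so the variance of the sex indicator is 0.25 × 0.75 = 0.1875.

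CI ratio (with sex / without) = √[s² / (s² + 0.1875 g²)] × t(36)/t(37)

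Neither g nor s is given. I assume g from 0 to 10 mm Hg and s from 8 to 10.46.

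| g (mm Hg) | s = 8 | s = 10.46 |
|---|---|---|
| 0 | 1.001 | 1.001 |
| 3 | 0.988 | 0.993 |
| 5 | 0.966 | 0.980 |
| 10 | 0.880 | 0.925 |

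Example, g = 5 and s = 8: √[64 / (64 + 4.69)] = 0.965; times the t ratio of 1.001 gives 0.966.

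**3. One baseline reading or two.** Assume equal correlation r between any two visits and an outcome that is the mean of two readings. Write v = (1 + r)/2. In units of single-reading variance, the residual variance is:
- one baseline reading: v − r²
- mean of two: v − r²/v

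| r | one | two | CI ratio | half-width if 10.46 is the one-reading residual SD |
|---|---|---|---|---|
| 0.3 | 0.560 | 0.512 | 0.956 | 6.70 to 6.41 |
| 0.5 | 0.500 | 0.417 | 0.913 | 6.70 to 6.12 |
| 0.7 | 0.360 | 0.274 | 0.872 | 6.70 to 5.84 |
| 0.8 | 0.260 | 0.189 | 0.852 | 6.70 to 5.71 |

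The interval is therefore 4% to 15% narrower. If the outcome were a single follow-up reading, as Protocol 9.4.1 can be read, the ratios would be 0.973, 0.943, 0.911 and 0.896: 3% to 10% narrower.

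**4. Effect of the eligibility limits.** Visit 1 SBP must lie in 100-149 mm Hg, which breaks the equal-correlation assumption. I used a simulation with 30 women and 10 men, permuted blocks within sex, an assumed mean of 130 and untruncated SD of 14, and 2,000 runs per setting. The mean half-width for both readings against Visit 3 alone was:
- r = 0.5: 6.21 to 5.82 (ratio 0.937, 6% narrower)
- r = 0.7: 5.29 to 4.73 (ratio 0.894, 11% narrower)

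At r = 0.3, with assumed means of 130-135 and SDs of 14-18, the variance falls only 4-6%. Since √0.96 = 0.980 and √0.94 = 0.970, the interval is 2-3% narrower. Against Visit 1 alone the figures in step 3 hold.

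**5. Is the test conservative without sex?** In the same simulation with g = 10 and the Visit 3 baseline, the reported SE against the empirical SE was 3.39 against 3.16 (r = 0.5) and 2.96 against 2.70 (r = 0.7). Type I error at nominal 5% was 3.8% and 2.9%. Monte Carlo error is about √(0.05 × 0.95 / 2000) = 0.5 percentage points. At g = 5 the rates were 3.8% and 5.5%, with no consistent shortfall.

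**The case against.** **The plan does not discard a reading.** A reader might infer that the model uses only one pre-diet reading and so must give wider intervals than the data allow. Neither document says so. The protocol calls Visit 1 the initial baseline visit and describes Visit 3 under Baseline Assessments, which fits a plan to use both. This objection stands: the defect is a missing definition, and the precision loss arises only if one reading is chosen.

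**Leaving out sex may cost nothing.** This also stands. The documents give no sex difference in SBP, and baseline BP may already absorb it. The reduced type I error appeared clearly only at the 10 mm Hg extreme. A reader might go further and call the analysis invalid or biased. It is neither: baseline-adjusted regression in a randomised intention-to-treat comparison gives an unbiased estimate here.

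**Hypertension treatment may not be a randomisation factor.** A reader might infer that a second stratification factor was dropped. But SAP 3.3 lists baseline antihypertensive use first among its pre-specified subpopulations, and the SAP contents page titles that section as a stratified analysis. The Protocol 3 sentence can mean that. Only a clarification is warranted.

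**The run-in reading may be contaminated.** Protocol 4.3 says "After baseline data collection, participants will be randomized in a 1:1 ratio to 1 of 2 meal plans", yet the schedule lists Visit 3 after the randomisation visit, with day labels that conflict (Visit 2 on Day 0, Visit 3 on Day -1 to -2). Protocol 6.2.2 puts randomisation at least 1-2 days before feeding. Protocol 4.3 says participants will know their assignment; 5.2 says they are blinded. If Visit 3 followed disclosure, its reading could be affected by assignment. This stands, and it makes the use of Visit 3 conditional.

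**Conclusion.** The point holds in two limited parts.

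- **Sex** is a stratification factor absent from the primary model. Including it matches the analysis to the design. The gain runs from nil (0.1% wider at worst) through 2-3% at a residual sex difference of 5 mm Hg to 8-12% at 10 mm Hg. These differences and the residual SD range are assumptions.
- **Baseline seated BP** is undefined. The firm part of the finding is the open analyst choice. The precision at stake is roughly 4-15% of CI width for assumed r of 0.3-0.8 if a single reading were chosen, and less against Visit 3 alone (6% at r = 0.5 and 11% at r = 0.7 in the truncated simulation).

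This concerns efficiency and pre-specification in a small pilot. The sample size is correct on its own inputs, and nothing here invalidates the primary analysis.

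**What to change.** In SAP 3.1 and Protocol 9.5:

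1. State the primary model as follow-up seated SBP on treatment, sex and baseline seated SBP.
2. Define baseline as the mean of the Visit 1 and Visit 3 readings, or enter both as separate covariates (reasonable given the truncation of Visit 1), provided the Visit 3 reading was taken before participants learned their assignment. Otherwise, use Visit 1 alone.
3. Establish from study records when Visit 3 fell relative to disclosure of assignment, and reconcile the visit-day labels in Protocol 6.1 and the masking statements in Protocol 4.3 and 5.2.
4. Say whether the Protocol 3 sentence on hypertension treatment refers to randomisation or to the subgroup analysis in SAP 3.3. Add that term to the model only if the randomisation list used it.

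The cost is a few sentences, one degree of freedom for sex (one more if both readings are entered separately), and a check of visit and randomisation dates. No new data are needed. The definitions should be fixed before anyone sees outcomes by arm.
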